2.8 Safety analyses

For all safety analyses, the safety set will be used. All listings and tables will be presented by treatment group. In addition, pooled safety analysis based on all subjects will be produced.

The overall observation period will be divided into three mutually exclusive segments:

1. pre-treatment period: from day of subject's informed consent to the day before first dose of study medication
2. on-treatment period: from day of first dose of study medication to 30 days after last dose of study medication
3. post-treatment period: starting at day 31 after last dose of study medication.

If dates are incomplete in a way that clear assignment to pre-, on-, or post-treatment period cannot be made, then the respective data will be assigned to the on-treatment period.

Safety will be assessed based on all treated subjects; toxicities will be defined by CTCAE v4.03. Incidence and severity of adverse events, causality attribution to drug, time to event onset, duration of the event, its resolution and concomitant medications administered will be recorded. Additional safety assessments will include laboratory safety assessment, vital signs, and cardiac assessment.

2.8.1 Adverse events (AEs)

AE summaries will include all AEs occurring during on treatment period. Additional summaries will be displayed to report all AEs, AEs related to study treatment, all SAEs and SAEs related to study treatment collected up to 150 days after last administration of PDR001. All AEs collected in the AE (e)CRF page will be listed along with the information collected on those AEs e.g. AE relationship to study drug, AE outcome etc. AEs with start date outside of on-treatment period will be flagged in the listings.

AEs will be summarized by number and percentage of subjects having at least one AE, having at least one AE in each primary system organ class (SOC) and for each preferred term (PT) using MedDRA coding. A subject with multiple occurrences of an AE will be counted only once in the respective AE category. A subject with multiple Common Terminology Criteria for Adverse Events (CTCAE) grades for the same preferred term will be summarized under the maximum CTCAE grade recorded for the event. AE with missing CTCAE grade will be included in the 'All grades' column of the summary tables.

In AE summaries, the primary system organ class will be presented alphabetically and the preferred terms will be sorted within primary SOC in descending frequency. The sort order for the preferred term will be based on their frequency in the total column.

The following adverse event summaries will be produced by treatment arm; overview of adverse events and deaths (number and % of subjects who died, with any AE, any SAE, any dose reductions/interruptions, leading to treatment discontinuation), AEs by SOC and PT, summarized by relationship (all AEs and AEs related to study treatment), seriousness (SAEs and non-SAEs), leading to treatment discontinuation, leading to dose interruption/adjustment, requiring additional therapy, requiring immunosuppressive medication and leading to fatal outcome. In addition, a summary of serious adverse events with number of occurrences will be

produced (an occurrence is defined as >1 day between start and prior end date of record of same preferred term).

For the legal requirements of clinicaltrials.gov and EudraCT, two required tables on on-treatment adverse events which are not serious adverse events with an incidence greater than and equal to 5% and on on-treatment serious adverse events and SAE suspected to be related to study treatment will be provided by system organ class and preferred term on the safety set population.

If for a same patient, several consecutive AEs (irrespective of study treatment causality, seriousness and severity) occurred with the same SOC and PT:

- a single occurrence will be counted if there is ≤ 1 day gap between the end date of the preceding AE and the start date of the consecutive AE
- more than one occurrence will be counted if there is > 1 day gap between the end date of the preceding AE and the start date of the consecutive AE

For occurrence, the presence of at least one SAE / SAE suspected to be related to study treatment / non SAE has to be checked in a block e.g., among AE's in a ≤ 1 day gap block, if at least one SAE is occurring, then one occurrence is calculated for that SAE.

The number of deaths resulting from SAEs suspected to be related to study treatment and SAEs irrespective of study treatment relationship will be provided by SOC and PT.

2.8.1.1 Adverse events of special interest / grouping of AEs

Adverse events of special interest (AESI) during the on-treatment period will be tabulated. The list of AESI will also include relevant events for spartalizumab, and the novel agents.

Data analysis of AESIs

An adverse event of special interest (AESI) is a grouping of adverse events that are of scientific and medical concern specific to compound PDR001, the individual novel agents, as well as combination specific AESIs (PDR001 + novel agent). These groupings are defined using MedDRA terms, SMQs (standardized MedDRA queries), HGLTs (high level group terms), HLT (high level terms) and PTs (preferred terms). Customized SMQs (Novartis MedDRA queries, NMQ) may also be used. A NMQ is a customized group of search terms which defines a medical concept for which there is no official SMQ available or the available SMQ does not completely fit the need. It may include a combination of single terms and/or an existing SMQ, narrow or broad. All AESI terms for the individual compounds as well as for combination specific AESIs are captured in the case retrieval strategy (CRS).

For each specified AESI, number and percentage of patients with at least one event of the AESI occurring during on treatment period will be summarized.

Summaries of these AESIs will be provided by treatment arm, (specifying grade, SAE, relationship, leading to treatment discontinuation, leading to dose adjustment/interruption, hospitalization, death, requiring immunosuppressive medication etc.). If sufficient number of events occurred, analysis of time to first occurrence will be applied.

Additional summaries will be provided to report all AESIs, AESIs related to study treatment, all serious AESIs and serious AESIs related to study treatment collected during the on-treatment period and up to 150 days after last administration of PDR001.

A listing of all grouping levels down to the MedDRA preferred terms used to define each AESI will be generated. This listing should be included in section 16 of CSR.

2.8.2 Deaths

Separate summaries for on-treatment and all deaths will be produced by treatment arm, system organ class and preferred term. Additional summary will be displayed to report all deaths up to 150 days after last administration of PDR001.

All deaths will be listed; post treatment deaths will be flagged. A separate listing of deaths prior to starting treatment will be provided for all screened subjects.

Note: "Study indication" as primary reason of death should be coded using MedDRA terms based on the diagnosis eCRF field at start of study. If not coded accordingly in the database, it still must be included in the summary table. Coded reasons for deaths will then be summarized by category 'Study indication' and 'Other' (as selected by the investigator).

The death summaries cover subjects from the Safety Set. The count of deaths in safety analyses could be different from the number of deaths in the efficacy analyses.

2.8.3 Laboratory data

Grading of laboratory values will be assigned programmatically as per National Cancer Institute (NCI) Common Terminology Criteria for Adverse Events (CTCAE) v4.03. The calculation of CTCAE grades will be based on the observed laboratory values only, clinical assessments will not be taken into account.

CTCAE Grade 0 will be assigned for all non-missing values not graded as 1 or higher. Grade 5 will not be used.

For laboratory tests where grades are not defined by CTCAE v4.03, results will be categorized as low/normal/high based on laboratory normal ranges.

The following summaries will be generated separately for hematology, and biochemistry tests:

- Listing of all laboratory data with values flagged to show the corresponding CTCAE v4.03 grades if applicable and the classifications relative to the laboratory normal ranges

For laboratory tests where grades are defined by CTCAE v4.03

- Worst post-baseline CTCAE grade (regardless of the baseline status). Each subject will be counted only once for the worst grade observed post-baseline.
- Shift tables using CTCAE v4.03 grades to compare baseline to the worst on-treatment value

For laboratory tests where grades are not defined by CTCAE v4.03

- Shift tables using the low/normal/high/ (low and high) classification to compare baseline to the worst on-treatment value.

On analyzing laboratory, data from all sources (central and local laboratories (as applicable)) will be combined. The summaries will include all assessments available for the lab parameter collected no later than 30 days after the last study treatment administration date (see Section 2.1.1).

The following summaries will be produced for hematology and biochemistry laboratory data (by laboratory parameter and treatment):

- Worst post-baseline CTCAE grade (regardless of the baseline status). Each subject will be counted only for the worst grade observed post-baseline.
- Shift tables using CTCAE grades to compare baseline to the worst on-treatment value
- For laboratory tests where CTCAE grades are not defined, shift tables using the low/normal/high/(low and high) classification to compare baseline to the worst on-treatment value.
- Trends of lab parameter values over time (baseline and selected on-treatment timepoints) should be displayed via boxplots based on time windows and corresponding tables displaying the statistics used for the box plots by the selected time points.

The following listings will be produced for the laboratory data:

- Listings of all laboratory data, with CTCAE grades and classification relative to the laboratory normal range. Lab data collected during the post-treatment period will be flagged.
- Listing of all CTCAE grade 3 or 4 laboratory toxicities

Liver function parameters

Liver function parameters of interest are total bilirubin (TBL), alanine aminotransferase (ALT), aspartate aminotransferase (AST) and alkaline phosphatase (ALP). The number (%) of patients with worst post-baseline values as per Novartis Liver Toxicity guidelines will be summarized:

The following summaries will be produced:

- ALT or AST > 3xULN
- ALT or AST > 5xULN
- ALT or AST > 8xULN
- ALT or AST > 10xULN
- ALT or AST > 20xULN
 - TBL > 2xULN
 - TBL > 3xULN
 - ALT or AST > 3xULN & TBL > 2xULN

- ALT or AST > 3xULN & TBL > 2xULN & ALP < 2xULN (potential Hy's law)

Potential Hy's Law events are defined as those subjects with concurrent occurrence of AST or ALT > 3xULN and TBL > 2xULN and ALP < 2xULN in the same assessment sample during the on-treatment period. Further medical review has to be conducted to assess potential confounding factor such as, liver metastases, liver function at baseline etc.

2.8.4 Other safety data

2.8.4.1 ECG and cardiac imaging data

Categorical Analysis of QT/QTc interval data based on the number of subjects meeting or exceeding predefined limits in terms of absolute QT/QTc intervals or changes from baseline will be presented. In addition, a listing of these subjects will be produced by treatment group.

Data handling

In case the study requires ECG replicates at any assessment, the average of the ECG parameters at that assessment should be used in the analyses.

Data analysis

12-lead ECG including PR, QRS, QT, QTcF, and RR intervals will be obtained for each subject during the study. ECG data will be read and interpreted centrally.

The number and percentage of subjects with notable ECG values will be presented by treatment arm.

- QT, QTcF
 - New value of > 450 and ≤ 480 ms
 - New value of > 480 and ≤ 500 ms
 - New value of > 500 ms
 - Increase from Baseline of > 30 ms to ≤ 60ms
 - Increase from Baseline of > 60 ms
- HR
 - Increase from baseline >25% and to a value > 100 bpm
 - Decrease from baseline >25% and to a value < 50 bpm
- PR
 - Increase from baseline >25% and to a value > 200 ms
 - New value of > 200 ms
- QRS
 - Increase from baseline >25% and to a value > 120 ms
- New values of QRS > 120 ms

A listing of all ECG assessments will be produced by treatment arm and notable values will be flagged. A separate listing of only the subjects with notable ECG values may also be produced. In the listing, the assessments collected during the post-treatment period will be flagged.

2.8.4.2 Vital signs

Vital sign assessments are performed in order to characterize basic body function. The following parameters were collected: height (cm), weight (kg), body temperature (°C), heart rate (beats per minute), systolic and diastolic blood pressure (mmHg).

Data handling

Vital signs collected on treatment will be summarized. Values measured outside of on treatment period will be flagged in the listings.

Data analysis

For analysis of vital signs the clinically notable vital sign criteria are provided in [Table 2-15](#) below.

Table 2-15 Clinically notable changes in vital signs

Vital sign (unit)	Clinically notable criteria	
	above normal value	below normal value
Weight (kg)	increase > 10% from Baseline	decrease > 10% from Baseline
Systolic blood pressure (mmHg)	>=180 with increase from baseline of >=20	<=90 with decrease from baseline of >=20
Diastolic blood pressure (mmHg)	>=105 with increase from baseline of >=15	<=50 with decrease from baseline of >=15
Pulse rate (bpm)	>=100 with increase from baseline of >25%	<=50 with decrease from baseline of > 25%
Body temperature	>= 39.1	-

[figure not shown]
The number and percentage of subjects with notable vital sign values (high/low) will be presented by treatment arm.

A listing of all vital sign assessments will be produced by treatment arm and notable values will be flagged. A separate listing of only the subjects with notable vital sign values may also be produced. In the listing, the assessments collected outside of on-treatment period will be flagged.

[REDACTED]

[REDACTED]

[REDACTED]

2.10 PD and [REDACTED] PD analyses

2.10.1 Immunogenicity

2.10.1.1 Sample ADA Status

Each IG sample is assessed in a three tiered anti-drug anti-body (ADA) testing approach. All IG samples are analyzed in the initial screening assay (first tier). Samples testing negative in the screening assay are not subject to a confirmatory assay. Samples testing positive in the screening assay are then subjected to the confirmatory assay to demonstrate that ADA are specific for the therapeutic protein product (second tier). The titer of confirmatory positive samples will be subsequently determined in the titration assay (third tier). Samples identified as positive in the confirmatory assay are considered ADA positive and are further characterized in the neutralization assay to indicate the presence of neutralizing antibodies (NAb). Samples can test negative in either the screening or confirmatory assay but for analysis purposes they are not differentiated. The following properties of each sample will be provided in the source data:

- Result of assay according to pre-specified confirmatory cut point: ADA positive (yes) or ADA negative (no)
- Titer (for positive samples): numerical representation of the magnitude of ADA response
- Presence of NAb (for positive samples, if NAb assay results are available): yes or no
- Drug tolerance level: highest drug concentration that does not interfere in the ADA detection method
- Fold titer change (i.e. x-fold): threshold for determining treatment boosted
- Sample ADA status is determined based on the following definitions:
 - *ADA-inconclusive sample*: Sample where assay is ADA negative [REDACTED] at the time of IG sample collection is greater than or equal to the drug tolerance level or missing.
 - *Unevaluable sample*: Sample where assay is not available.
 - *Determinant sample*: Sample that is neither ADA-inconclusive nor unevaluable.

The following definitions apply only to determinant samples:

- *ADA-negative sample*: Determinant sample where assay is ADA negative [REDACTED] at the time of IG sample collection is less than the drug tolerance level.
- *ADA-positive sample*: Determinant sample where assay is ADA positive.
- *ADA-positive NAb sample*: Determinant sample where assay is ADA positive and presence of NAb = yes.

The following definitions apply only to post-baseline ADA-positive samples with a corresponding determinant baseline sample. To be classified as *treatment-boosted* or *treatment-unaffected*, both the post-baseline and baseline titer must be non-missing:

- *treatment-induced ADA-positive sample*: ADA-positive sample post-baseline with ADA-negative sample at baseline.

- *treatment-boosted ADA-positive sample*: ADA-positive sample post-baseline with titer that is at least *the fold titer change* greater than the ADA-positive baseline titer.
- *treatment-unaffected ADA-positive sample*: ADA-positive sample post-baseline with titer that is less than *the fold titer change* greater than the ADA-positive baseline titer

The following summaries of ADA sample status (n and %) will be provided using *Immunogenicity prevalence set*:

- ADA-positive samples (i.e. ADA prevalence) and ADA-positive NAb samples, both overall and by time point (including baseline). For summaries by time point, the denominator is the number of subjects at that time point with a determinant sample.

Listings will be provided of sample ADA status (including titer for positive samples).

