2.2 Analysis sets

All below defined analysis sets will be used to analyze data from both the selection phase (part 1) and the expansion phase (part 2).

Full Analysis Set

The Full Analysis Set (FAS) comprises all subjects to whom study treatment has been assigned by randomization. According to the intent to treat principle, subjects will be analyzed according to the treatment they have been assigned to during the randomization procedure regardless of whether or not treatment was administered. This population will be the primary population for efficacy analysis.

Per protocol set (PPS)

Not applicable.

Safety

The Safety Set includes all subjects who received at least one dose of study treatment. Subjects will be analyzed according to the study treatment received, where treatment received is defined as the randomized treatment if the subject took at least one dose of that treatment or the first treatment received if the randomized treatment was never received.

The actual treatment received corresponds to:

- the randomized treatment if patients took at least one dose of that treatment.
- the first treatment received if the randomized treatment was never received

Note: if a patient is assigned to a dose level for instance, PDR001 400 mg and just receives partial infusion of the treatment, the patient will still be analyzed under PDR001 400 mg treatment arm for safety analysis.

Biomarker analysis set

The biomarker analysis set, as it pertains to the secondary objective (Section 10.5.5 of the protocol), consists of all subjects in the safety set with an evaluable baseline tumor biopsy sample and at least one evaluable post-baseline tumor biopsy sample. [REDACTED]

Immunogenicity (IG) analysis sets

The *Immunogenicity prevalence set* includes all subjects in the Full analysis set with a determinant baseline IG sample **or** at least one determinant post-baseline IG sample.

The *Immunogenicity incidence set* includes all subjects in the Immunogenicity prevalence set with a determinant baseline IG sample **and** at least one determinant post-baseline IG sample.

See [Section 2.10.1.1](#) for the definition of *determinant*.

Patient Classification:

Patients may be excluded from the analysis populations defined above based on the protocol deviations entered in the database and/or on specific subject classification rules defined in [Table 2-4](#).

Table 2-4 Subject classification based on protocol deviations and non-PD criteria

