2.10.1.2 Subject ADA status

Any IG sample collected after 150 days of the last dose of PDR001, LAG525, or Canakinumab will not be used for summaries or derivations and will only be included in the listing.

Subject ADA status is defined as follows:

- *Treatment-induced ADA-positive subject*: subject with ADA-negative sample at baseline and at least one treatment-induced ADA-positive sample.
- *Treatment-boosted ADA-positive subject*: subject with ADA-positive sample at baseline and at least one treatment-boosted ADA-positive sample.
- *Treatment-unaffected ADA-positive subject*: subject with ADA-positive sample at baseline, no treatment-boosted ADA-positive samples, and at least one treatment-unaffected ADA-positive sample.
- *Treatment-reduced ADA-positive subject*: subject with ADA-positive sample at baseline and at least one post baseline determinant sample, all of which are ADA-negative samples.
- *ADA-negative subject*: subject with ADA-negative sample at baseline and at least one post baseline determinant sample, all of which are ADA-negative samples.
- *Inconclusive subject*: subject who does not qualify as treatment-induced ADA-positive, treatment-boosted ADA-positive, treatment-unaffected ADA-positive, treatment-reduced ADA-positive, or ADA-negative.

The following summaries of ADA subject status (n and %) will be provided using *Immunogenicity incidence set*:

- Treatment-boosted ADA-positive subjects; denominator is the number of subjects with ADA-positive sample at baseline.

- Treatment-induced ADA-positive subjects; denominator is the number of subjects with ADA-negative sample at baseline.
- ADA-negative subjects: denominator is the number of subjects in *Immunogenicity incidence set*.
- ADA-positive subjects (i.e. ADA incidence): calculated as the number of treatment-boosted ADA-positive and treatment-induced ADA-positive subjects; denominator is the number of subjects in *Immunogenicity incidence set*.

Listings will be provided of subject ADA status.

[REDACTED]

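### ADA rates drop some negative samples but no positives: on-treatment prevalence can be overstated, incidence can err either way, and no visible table counts the inconclusive results

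*SAP*

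**What the plan says.** All references are to the SAP for the randomized part unless stated.

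- **Sample status (2.10.1.1).** An assay-negative sample is ADA-inconclusive when a redacted quantity "at the time of IG sample collection is greater than or equal to the drug tolerance level or missing". A determinant sample is a "Sample that is neither ADA-inconclusive nor unevaluable". An ADA-positive sample is a "Determinant sample where assay is ADA positive", with no condition on drug level. The tolerance level is the "highest drug concentration that does not interfere in the ADA detection method"; no value is given.
- **Prevalence (2.10.1.1).** "For summaries by time point, the denominator is the number of subjects at that time point with a determinant sample". Baseline is one of the time points. The denominator of the overall sample summary is not stated.
- **Analysis sets (2.2).** The prevalence set "includes all subjects in the Full analysis set with a determinant baseline IG sample" or at least one determinant post-baseline sample. The incidence set "includes all subjects in the Immunogenicity prevalence set with a determinant baseline IG sample" and at least one determinant post-baseline sample.
- **Incidence (2.10.1.2).** It is "calculated as the number of treatment-boosted ADA-positive and treatment-induced ADA-positive subjects", divided by the incidence set. Samples up to 150 days after the last dose are used. One determinant post-baseline sample is enough to class a baseline-negative subject as ADA-negative, provided every determinant sample is negative.
- **Endpoint (Table 1-1).** ADA prevalence at baseline and ADA incidence on treatment.
- **Arm 1A SAP (2.2).** It takes its definition of determinant from the main SAP, so the rule carries over.

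Inconclusive samples and inconclusive subjects are both defined. In the legible text, however, ADA status is only listed, and no summary counts either category.

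**The concern.** Whether an available assay result enters the denominator depends on the result itself: only negatives can be removed. Study drug is absent before the first dose and present afterwards, so the tolerance filter acts unevenly over time. A table of positivity by time point could then show a rise from baseline that comes partly from assay interference, and the reader would have no count of what was removed.

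The rule for missing measurements is a separate problem. It also applies to pre-first-dose samples, where no study drug has been given and there is nothing to interfere. A baseline-negative subject whose measurement is missing leaves the incidence set, and cannot be classed as treatment-induced because that needs an ADA-negative baseline sample. A baseline-positive subject with the same missing value stays.

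**Working it through.** The SAP states no ADA rate, tolerance value or sample count, so it has no figure to reproduce. Every input below is an assumption, and ranges are shown.

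**1. By-time-point prevalence.** Let p be the true ADA-positive share, h the share of samples with drug at or above tolerance, and s the probability that a true positive is still detected above tolerance (1 below it). ADA is first taken to be unrelated to drug level. A missed positive above tolerance reads as negative, so it too becomes inconclusive.

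- Determinant-only rate = p(1−h+hs) / [p(1−h+hs) + (1−p)(1−h)]
- Rate over all available results = p(1−h+hs)

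With p = 0.05 and h = 0.5:

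- s = 0: 0.025/(0.025 + 0.475) = 5.0%; over all results 2.5%
- s = 0.5: 0.0375/(0.0375 + 0.475) = 7.3%; over all results 3.8%
- s = 1: 0.05/(0.05 + 0.475) = 9.5%; over all results 5.0%

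Determinant-only rate over a range of h, p = 5%:

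| h | s = 0 | s = 0.5 | s = 1 |
|---|---|---|---|
| 0.3 | 5.0% | 6.0% | 7.0% |
| 0.5 | 5.0% | 7.3% | 9.5% |
| 0.8 | 5.0% | 13.6% | 20.8% |

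If ADA goes with lower drug levels, the rate is overstated even at s = 0. With true positives half as likely to be above tolerance (0.25 against 0.5), it is 0.05×0.75/(0.05×0.75 + 0.95×0.5) = 7.3%.

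**2. Incidence.** Assume 5% of subjects truly become positive, all baselines are determinant negative, there are four on-treatment samples each above tolerance with probability h = 0.8 independently, and a drug-free washout sample is available with probability w. A subject with no ADA has at least one determinant sample with probability 1 − 0.8⁴(1−w): 0.5904, 0.7952 and 0.9590 for w = 0, 0.5 and 0.9.

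- Persistent ADA, s = 1: 0.05/(0.05 + 0.95×0.5904) = 8.2%. At w = 0.5 it is 6.2% and at w = 0.9 it is 5.2%.
- Persistent ADA, s = 0: numerator and denominator shrink together, giving 5.0% throughout.
- Transient ADA (one on-treatment sample only), s = 0: the positive sample is seen with probability 0.2, so 0.05×0.2/0.5904 = 1.7%. At w = 0.5 it is 1.3% and at w = 0.9 it is 1.0%.

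So a true 5% can be reported as 8.2% or as 1.0%. In the transient case, dividing by all subjects gives 0.05×0.2 = 1.0%, so both rates lie below the truth.

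**3. Missing measurement before the first dose.** No study drug is present, so positives are not masked by it. If a share m of baseline measurements is missing regardless of ADA status, reported baseline prevalence is p/[p + (1−p)(1−m)]. With p = 5%, that is 0.05/(0.05 + 0.95×0.9) = 5.5% at m = 0.1 and 0.05/(0.05 + 0.95×0.7) = 7.0% at m = 0.3.

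**The case against.** A negative result at or above the tolerance level cannot be interpreted, because drug may be hiding antibody. Setting it aside is a defensible rule, and counting it as negative has its own bias: 2.5% against a true 5% in the case h = 0.5, s = 0. This stands, and it is why the determinant-only rate should stay.

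A reader might infer three stronger things that the document does not support.

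- **That prevalence is inflated by construction.** It is not. If drug fully masks positives above tolerance and ADA is unrelated to drug level, the determinant-only rate is unbiased at every h.
- **That incidence is inflated.** The direction is open. A single determinant post-baseline sample is enough, washout samples can supply it, and transient ADA can be missed. Nor does incidence keep every positive: a post-baseline positive with an inconclusive baseline is excluded from the incidence set, and a baseline positive with a missing titer cannot be classed as boosted but stays in the denominator.
- **That arms or drugs with higher exposure would look more immunogenic.** Higher exposure also masks positives, so the sign is not determined.

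It is also fair that the prevalence endpoint in Table 1-1 is at baseline, where the rule acts mainly through missing values. The analysis is secondary and descriptive, individual status is listed, and for arm 1A the immunogenicity sets are outside the interim analyses. These points limit the consequence. They do not supply the missing counts or justify the pre-dose rule.

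**Conclusion.** The point holds in a conditional form. The definitions remove only negatives from the sample-level denominators. By-time-point prevalence on treatment can therefore be overstated relative to baseline when some positives are detected above tolerance, or when ADA goes with lower drug levels. For an assumed true 5% with half of samples above tolerance, and ADA unrelated to drug level, the reported rate runs from 5.0% to 9.5% according to how many of those positives are detected. Incidence can err in either direction. The pre-dose missing-value rule treats negatives and positives differently without an interference rationale, whatever the assay's behaviour; its size depends on how often the measurement is missing, which the document does not say.

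Two assumptions matter: that the redacted quantity is drug concentration, inferred from its comparison with the tolerance level, and that no redacted table already reports inconclusive counts. The main practical gap is that a reader of the visible planned tables cannot tell how many results were set aside.

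**What to change.** 1. In 2.10.1.1, classify a pre-first-dose ADA-negative sample with a missing measurement as determinant negative.
2. Report n (%) of inconclusive samples by arm and time point, and n (%) of inconclusive subjects by arm.
3. Beside each determinant-only rate, give positives over all subjects with an available assay result. Label it as a supportive lower figure, not a replacement, and do not say that the two rates bracket the true incidence.

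The arm 1A SAP takes its definition from the main SAP, so the wording change carries over; its tables need the same rows. The cost is a sentence or two of SAP text and a few table rows, with no new data collection. The drawback is that the supportive rate is too low if drug masks true positives, which a footnote should say.
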